### 9.2.1. Criteria for inclusion

Patients must satisfy all of the following criteria for inclusion in order to be eligible.

- Male or female patient 18 years of age or older;
- Patient with BCR-ABL Philadelphia chromosome positive or negative CML, in chronic, accelerated or blast phase;
- Patient resistant or intolerant to previous therapy with TKI for CP, AP or CB CML other than bosutinib;
- Patient initiating treatment with bosutinib for treatment of CP, AP or BP phase Ph+ / - CML at the end of the inclusion visit or during the one month prior to it;
- Patient who has been informed that a method of contraception must be used if a risk of pregnancy exists.
- Patients who have been informed about the study and who signed the informed consent form.

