**Progression**

Defined as passage from the chronic phase to the accelerated phase or to blast phase. This progression must be validated by two consecutive evaluations less than one week apart. Patients presenting an increase in leukocyte count in at least one period greater than or equal to one month, with second assay measurement  $> 20 \times 10^9/L$  and confirmed at least one week later. Patients presenting a loss of major hematological response (with hematological confirmation within a time greater than or equal to 2 weeks after loss of initial response) or non-confirmation of major cytogenetic response (with a Ph+ rate increased by 30%).

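### The leukocyte progression criterion sets no minimum rise and no reference value, so patients with counts near or above 20 x10^9/L can progress on fluctuation alone; the cytogenetic criterion leaves its 30% undefined and unconfirmed

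*Protocol*

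**What the plan says.** Section 9.7.3 (Progression) begins with transformation from chronic phase to accelerated or blast phase, then adds further routes.

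- **Leukocytes:** "Patients presenting an increase in leukocyte count in at least one period greater than or equal to one month", "with second assay measurement" above 20 x10^9/L "and confirmed at least one week later". No size of rise is given, and nothing says whether the increase is measured from baseline, from the lowest value or from the previous visit.
- **Haematological response:** loss of a major response, "with hematological confirmation within a time greater than or equal to 2 weeks after loss of initial response".
- **Cytogenetic response:** "non-confirmation of major cytogenetic response (with a Ph+ rate increased by 30" per cent. The scale of the 30% is not stated and no repeat sample is asked for.

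Section 9.2.1 admits a "Patient with BCR-ABL Philadelphia chromosome positive or negative CML, in chronic, accelerated or blast phase" and a "Patient resistant or intolerant to previous therapy with TKI for CP, AP or CB CML other than bosutinib". Neither 9.2.1 nor 9.2.2 limits the leukocyte count.

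Still in 9.7.3, PFS runs from the start of bosutinib to progression, dated by the participating doctor, or death. Duration of response ends at confirmed loss of response, progression or death. Visits are expected about every 3 months for 3 years (section 9.1), which gives 12 follow-up visits (Table 4).

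**The concern.** A progression rule should separate real worsening from measurement and day-to-day variation. Here the level of 20 x10^9/L is the only thing that separates them. A patient who starts above 20 meets the level from the first visit, and any later value that happens to be higher supplies the increase. Readings of 25, then 26, then 26 qualify. So do 100, 30, 32 and 33 if the reference is the previous visit, although that patient has improved greatly. The confirmation repeats the level but has no size of rise to repeat.

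The cytogenetic criterion has a related fault. Non-confirmation of a response is not the same as loss of a documented one, and a 30% rise means different things on the relative and percentage-point scales. With no repeat sample, one unconfirmed test could end a duration of response through the progression route, even though that endpoint otherwise asks for confirmed loss.

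At stake are PFS at 1, 2 and 3 years and duration of response, which false events would shorten. Patients who enter in accelerated or blast phase cannot have the transformation event as defined, so for them the other criteria are the only progression events short of death. High counts at entry are also most plausible in those patients and in resistant patients.

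**Working it through.** The protocol gives no error rate for this definition. Its only design figure is a 95% half-width of at most 10% with 100 patients (section 9.5). That reproduces, 1.96 x sqrt(0.5 x 0.5/100) = 9.8%, and has no bearing here.

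**Leukocytes: set-up.** Take a patient whose true count does not change. From the protocol: quarterly visits, 12 in all, level 20, confirmation required. Assumed: independent lognormal variation with CV 10, 20 or 30%. An event requires the visit value and the confirming value both to exceed 20 and both to exceed the reference. This is a strict reading of confirmation.

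**Exact ceiling far above 20.** When the level is always met, one visit qualifies if the reference is the smallest of three exchangeable values, which has probability 1/3 whatever the CV. With a baseline reference, the probability of at least one event in k visits is 1 minus the product of 2j/(2j+1) for j = 1 to k:
- k = 4: 1 - (2 x 4 x 6 x 8)/(3 x 5 x 7 x 9) = 1 - 384/945 = 59.4%
- k = 12: 1 - 0.248 = 75.2%

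**Simulation with the level applied, four quarterly visits:**

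| True count | Reference | CV 10% | CV 20% | CV 30% |
|---|---|---|---|---|
| 22 | baseline | 59% | 56% | 53% |
| 22 | previous visit | 83% | 72% | 64% |
| 25 | baseline | 59% | 59% | 58% |
| 25 | previous visit | 86% | 84% | 78% |

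Over all 12 visits at a count of 25, the figures are about 75% (baseline) and 99-100% (previous visit).

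**Same rule at lower counts, 12 visits:**
- 8 to 12: 0 to 1%
- 15: 0, 4 and 17% for CV 10, 20 and 30%
- 18: about 18%, 48-52% and 57-63%

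The problem is therefore confined to counts near or above 20.

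**Effect of a minimum rise.** A doubling is used for illustration, with the doubling itself confirmed; true count 25, 12 visits:

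| Reference for doubling | CV 10% | CV 20% | CV 30% |
|---|---|---|---|
| baseline | 0% | 0.7% | 7% |
| previous visit | 0% | 0.9% | 13% |
| lowest on-treatment value | 0% | 4% | 37% |

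The choice of reference matters as much as the size of the rise.

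**Cytogenetics.** Assumed: 20 metaphases per test, major response = Ph+ of at most 35% (7 of 20 or fewer), stable true Ph+ rate p. Using exact binomial probabilities, divide P(first test at most 7, second above 7 with the required rise) by P(first test at most 7):

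| p | P(first at most 7) | 30% relative | 30 percentage points |
|---|---|---|---|
| 10% | 0.9996 | 0.0004/0.9996 = 0.04% | 0.0003/0.9996 = 0.03% |
| 20% | 0.968 | 0.0295/0.968 = 3.0% | 0.0094/0.968 = 1.0% |
| 30% | 0.772 | 0.1463/0.772 = 18.9% | 0.0267/0.772 = 3.5% |

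Exactly on the assumed limit (p = 35%, P(first at most 7) = 0.601) the figures would be 0.1887/0.601 = 31% and 0.0327/0.601 = 5.4%.

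**The case against.** The strongest reply is that PFS uses the doctor's date of progression, so nobody may ever apply the listed criteria mechanically. A doctor would hardly call 25, 26, 26 a progression, or a fall from 100 to the low 30s. This stands in part: clinical judgement may soften the rule. But the PFS paragraph does not replace the definition, and the protocol does not say which prevails. About twenty centres could then each apply their own threshold.

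Second, the leukocyte figures hold the true count at 22 to 25 throughout. Many patients will not stay there: intolerant patients are eligible, and section 7.3 reports complete haematological response in 86% and 73% of the two chronic-phase groups of study 200. This stands. A reader might infer that noise creates progressions across the whole cohort. The documents do not support that, because at counts of 8 to 12 the rate is practically nil.

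Third, a reader might infer that bare non-confirmation counts as cytogenetic progression, or that the cytogenetic criterion is as noisy as the leukocyte one. Neither follows. The text also requires "with a Ph+ rate increased by 30" per cent, and at a stable Ph+ of 20 to 30% the percentage-point reading stays at or below 3.5%. The protocol is also visibly a translation, and non-confirmation may simply render loss. That is a reason to clarify the wording, not evidence of an intended endpoint.

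Fourth, the affected endpoints are secondary and descriptive. The primary endpoints in 9.7.2 are untouched, and phases are described separately (9.7.1) with no planned PFS comparison between them. A claim that a phase comparison is distorted would go too far.

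**Conclusion.** The point holds for patients with leukocyte counts near or above 20 x10^9/L. This goes beyond missing detail that an analysis plan could supply: the rule as stated accepts any increase. At a stable count of 22 to 25 it is met without any real change in about 53-59% of patients over four quarterly visits with a baseline reference, and in 64-86% with a previous-visit reference. The CV of 10-30% and the independence of visits are assumptions, but the baseline ceiling of 59.4% well above the level does not depend on the CV.

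The cytogenetic criterion is ambiguous and unconfirmed. At a stable Ph+ of 20 to 30% its false rate per test is about 3-19% on the relative reading and 1-3.5% in percentage points, assuming 20 metaphases and a 35% limit.

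The total bias in PFS and duration of response cannot be stated, because the share of patients above 20 is not in the protocol. The definition should be corrected before these secondary endpoints are derived.

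**What to change.** In section 9.7.3 (Progression):

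1. Name the reference value for the leukocyte increase and require a minimum rise larger than within-patient variation, with that same rise, and not only the level, confirmed at least one week later. The sponsor should choose the threshold after checking its false-event rate over the 12 planned visits. In the illustration above, a doubling from baseline gives 0-7%, but a doubling from the lowest value gives up to 37%.
2. Replace non-confirmation by confirmed loss of a previously documented major cytogenetic response, with the 30% stated in percentage points.
3. In the PFS paragraph, state whether the listed criteria or the doctor-estimated date decides the event.

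The cost is a few sentences and the matching derivation; the leukocyte change needs no new data collection. Because the study adds no examinations, cytogenetic confirmation has to come from the next routine test, so some events would be confirmed late. The other drawback is that some true but smaller rises from a high starting count, for example 80 to 150 under a doubling rule, would be dated later or not counted by the leukocyte criterion. The sponsor should weigh this when setting the threshold.

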**Progression-free survival at 1, 2 and 3 years of patients treated with bosutinib:**

Progression-free survival will be defined as the duration between initiation of bosutinib and date of progression estimated by the participating doctor or death of patient (all causes combined) (Kaplan Meier method).

**Overall survival at 1, 2 and 3 years of patients treated with bosutinib:**

Overall survival will be defined as the duration between initiation of bosutinib and date of death (all causes combined) (Kaplan Meier method).

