POPULATION CONCERNED:	
Criteria for inclusion:
 
 
• Male or female patient 18 years of age or older;
 
• Patient with Philadelphia chromosome positive or negative CML, or BCR-ABL positive, chronic, accelerated or blast phase;
 
• Patient resistant or intolerant to previous therapy with a TKI for CP, AP or BP CML other than bosutinib;
 
• Patient initiating bosutinib for treatment of CP, AP or BP Ph+/- CML, at the end of the inclusion visit or during the month preceding it;
 
• Patient who has been informed that a method of contraception must be used if a risk of pregnancy exists;
 
• Patient who has been informed about the study and who signed his or her consent form.
 
 
Criteria for non-inclusion:
 
 
• Patient with Philadelphia chromosome
 

	
negative CML, BCR-ABL negative chronic, accelerated or blast phase CML.
 
 
• Patient recently diagnosed with CML and who has not received previous treatment with TKI;
 
• Patient currently treated with a treatment other than bosutinib
 
• Patient of childbearing potential not using a method of contraception;
 
• Patient treated in the setting of an interventional study for another disease (outside of follow-up period);
 
• Patient who refuses computer processing of his/her medical data.
 

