## 7. RATIONALE AND GENERAL CONSIDERATIONS

### 7.1. Chronic myeloid leukemia

Chronic myeloid leukemia (CML) is a malignant hematological disease which belongs to the group of myeloproliferative syndromes (or myeloproliferative neoplasia according to WHO classification 2008 [1]). This hematologic disease is a rare disease, with 600 to 700 new cases per year (the incidence in France is estimated at 1 or 2 cases per 100,000 persons, and increasing with age) [2], accounting for 15% to 20% of all cases of leukemia [3]. Mean age at time of diagnosis is 54 years and the disease affects 1.4 males vs. 1 female patient. The prevalence, on the order of 6000 to 7000 patients in France, is on the increase because of a frank decrease in mortality rate, at least during the first 6 years after the diagnosis [2].

CML results from a specific chromosomal anomaly which occurs in hematopoietic stem cells, although the principal cause of this anomaly is not yet understood. It is characterized by the presence of a chromosomal marker in hematopoietic cells, the Philadelphia chromosome (Ph1 chromosome), which can be detected in 95% of patients with CML [4]. The chimeric protein BCR-ABL (Breakpoint Cluster Region – Abelson), resulting from

translocation t(9; 22) at the origin of the Philadelphia chromosome positive (Ph+), has a high tyrosine kinase activity responsible for leukemic transformation by resulting in excessive and persistent production of white blood cells.

The disease, referred to as chronic, develops gradually and evolves slowly in three successive phases, becoming increasingly resistant to treatments with progression of disease: chronic phase (CP CML), accelerated phase (AP CML) and blast phase (blast crisis) (BP CML). The majority of patients are diagnosed during the chronic phase. Without treatment, patients in chronic phase CML will progress to the accelerated phase in 4 to 6 years. Patients diagnosed during the accelerated phase have a life expectancy estimated at less than 12 months in the absence of treatment. Following the blast phase, patients live on average 2 to 4 months if they are not treated [4].

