### **9.1. Study design**

This is a national, observational, descriptive, prospective, multicentre study conducted in metropolitan France in adult patients treated for accelerated or blast phase Philadelphia chromosome positive chronic myeloid leukemia, previously treated with one or more TKIs and for whom imatinib, nilotinib and dasatinib are not considered as appropriate treatments. The study will be conducted in all centres involved in management of CML, i.e. about twenty (20) in expected centres.

[figure not shown]
The study will be offered to the totality of patients who satisfy criteria for inclusion and for non-inclusion up to the end of the inclusion period defined as 4 years. About one hundred

(100) patients included are expected in the study. Therapeutic management of a patient will not be changed by participation in the study and will depend on decisions taken by doctors in agreement with current international recommendations (European Leukemia Net, ELN network [13]) (see paragraph 7.3).

Patients will be followed prospectively over a 3-year period starting with their inclusion in the study. The inclusion visit will be performed at time of inclusion of the patient in the study, after which the patient has been informed and has accepted to participate by signing the consent form. Follow-up visits will be performed after usual consultation, estimated at about every 3 months. No visit or additional examination will be requested by the protocol: modalities for follow-up and treatment will be left up to the entire judgement of the participating doctor. Data will be recorded during the 3 years of the patient's participation, except in case of withdrawal of consent, death of a patient or termination of the study before its planned end.

Total duration of the study is estimated at 7 years with an inclusion period of 4 years and a follow-up period of 3 years (see Figure 1). Throughout the study, at least one monitoring visit per year will be performed.

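### Overall survival is counted from the first bosutinib dose, but patients may be included up to a month later and must be alive to consent, so early starters bias it slightly upward

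*Protocol*

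**What the plan says.** **Entry.** Protocol section 9.2.1 admits a patient who starts bosutinib "at the end of the inclusion visit or during the one month prior to it"; the synopsis gives the same window, "at the end of the inclusion visit or during the month preceding it". The same list requires "Patients who have been informed about the study and who signed the informed consent form". Section 11.3 also expects that some patients will already be exposed to bosutinib when they consent.

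**Start of observation.** Section 9.1: "Patients will be followed prospectively over a 3-year period starting with their inclusion in the study".

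**Time origin and estimator.** Section 9.7.3: "Overall survival will be defined as the duration between initiation of bosutinib and date of death", and likewise "Progression-free survival will be defined as the duration between initiation of bosutinib and date of progression estimated by the participating doctor" or death. Both use Kaplan-Meier and are to be given at 1, 2 and 3 years. Treatment duration, in the same section, also runs from initiation with Kaplan-Meier curves. Section 9.7.1 adds the median with its 95% confidence interval, and results are described separately by disease phase.

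The protocol mentions neither delayed entry nor an analysis restricted to patients who start at the inclusion visit. The limitations in section 9.9 do not raise the point.

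**The concern.** The clock starts at the first dose, but the study can observe a patient only from inclusion. For anyone who started earlier, the gap between the two dates is free of death by construction, because someone who died in the gap could not be included. Kaplan-Meier run from initiation without delayed entry nevertheless counts these patients as at risk in the gap. Deaths that would belong to that period are missing from the numerator while the survivors sit in the denominator. This is left truncation, and for OS the bias can only be upward.

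The effect depends on the share of early starters, the length of the gap and the death rate in the first month. Blast phase is where it could be visible. Section 7.1 says of that phase: "Following the blast phase, patients live on average 2 to 4 months if they are not treated". Because survival is reported by phase, the blast-phase estimate would stand on its own and would not be diluted by the chronic-phase patients.

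**Working it through.** **Inputs from the protocol**
- Gap between first dose and inclusion: 0 to 1 month (9.2.1).
- Reporting times: 1, 2 and 3 years (8.2, 9.7.3), plus the median (9.7.1).
- Untreated survival (7.1): blast phase 2 to 4 months on average; accelerated phase under 12 months.
- Planned size: about 100 patients (9.5).

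**Assumptions (not in the protocol)**
- Exponential survival.
- Share *f* of initiators included late: 25% to 100%.
- Gap either a full month or uniform on 0 to 1 month.
- Treated blast-phase median of 6 to 11 months; chronic-phase 3-year OS of 80% to 90%.

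**1. The plan's own precision figure.** 1.96 × √(0.5 × 0.5 / 100) = 9.8 points. This agrees with section 9.5. Greenwood's formula without censoring gives the same value at 50% survival.

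**2. Formula for the bias.** For *t* beyond one month,

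S_naive(t) = S(t) / [(1 − f) + f × P(alive at inclusion)].

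If everyone enters a full month late, this becomes S(t)/S(1), which for exponential survival equals S(t − 1).

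**3. Largest error at the planned times.** Write *q* for monthly survival. With f = 1 and a full month's gap the error is q^(t−1) − q^t, which is largest at q = (t − 1)/t:
- 1 year: (11/12)^11 / 12 = 3.2 points
- 2 years: (23/24)^23 / 24 = 1.6 points
- 3 years: (35/36)^35 / 36 = 1.0 point

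The median moves by exactly one month in this extreme case and by less otherwise. If half enter late with a uniform gap, the 1-year error is about 0.8 point at most.

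**4. By phase.** The lower naive value has 25% late with a uniform gap; the upper has all patients a full month late.

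| Setting | True 1-year OS | Naive 1-year OS | True median (months) | Naive median (months) |
|---|---|---|---|---|
| Blast, untreated mean 2 months | 0.2% | 0.3–0.4% | 1.4 | 1.5–2.4 |
| Blast, untreated mean 4 months | 5.0% | 5.1–6.4% | 2.8 | 2.9–3.8 |
| Blast, assumed median 6 months | 25.0% | 25.4–28.1% | 6.0 | 6.1–7.0 |
| Blast, assumed median 11 months | 46.9% | 47.3–50.0% | 11.0 | 11.1–12.0 |
| Accelerated, mean 12 months | 36.8% | 37.2–40.0% | 8.3 | 8.4–9.3 |
| Chronic, assumed 3-year OS 80% | 92.8% | 92.9–93.4% | beyond 3 years | – |
| Chronic, assumed 3-year OS 90% | 96.5% | 96.6–96.8% | beyond 3 years | – |

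**5. Does delayed entry remove it?** A simulation of 400,000 initiators (median 6 months, half late, uniform gap) gave:

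| OS at | True | Kaplan-Meier from initiation | With delayed entry |
|---|---|---|---|
| 6 months | 50.0% | 51.4% | 49.9% |
| 12 months | 25.0% | 25.7% | 25.0% |

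**6. Against sampling error.** The worst 1-year error of 3.2 points compares with a half-width of 9.8 points for 100 patients. The protocol gives no blast-phase number. If it were 10, the Wald half-width at 25% survival would be 1.96 × √(0.25 × 0.75 / 10) = 26.8 points.

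**The case against.** **The detail belongs in the statistical analysis plan.** Section 9.7.3 ends by deferring detail on the secondary objectives to that plan, and section 9.7 allows it to change the protocol's analyses. This has some force: the plan is not at hand and may already specify delayed entry. But the protocol itself fixes both the origin and the estimator, and a plan that followed them literally would carry the bias.

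**The error is small against the noise.** This stands. Only early starters are affected, for at most a month, no hypothesis is tested and neither primary objective is touched. A confidence interval does not reveal or correct an error that always runs one way, however, so the point survives as a correction of method.

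**Stronger readings that the documents do not support**
- *A large distortion of blast-phase survival.* At 6 months, with an untreated mean of 4 months, OS could read 28.7% instead of 22.3%. But 6 months is not a planned reporting time, and section 7.1 gives an average for untreated patients, whereas this cohort is treated by definition.
- *PFS and treatment duration are guaranteed event-free before inclusion.* Only death is ruled out. A patient who progressed, or who stopped bosutinib and takes nothing else, can still meet the criteria. Section 9.2.2 bars patients on another treatment; it does not require that bosutinib is still being taken.
- *The non-inclusion registry cannot record early deaths.* The instructions in Annex 3.7 speak of patients who did not want to take part. Sections 9.4.1.7 and 9.5, however, ask for all eligible patients not included, and the form has a free-text reason. Capture of early deaths is unclear, not excluded.

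**Conclusion.** The point holds for OS and for the death component of PFS. The entry window and the time origin do not match, and Kaplan-Meier as described overstates survival for patients who started before inclusion. The upper limits of about 3.2, 1.6 and 1.0 points at 1, 2 and 3 years, and of one month on the median, rest on exponential survival with every patient included a full month late. The actual share and gap are not stated, and the real error is probably well below these limits. The limits depend on the model: if the death rate were higher in the first month than later, the error at the planned times could exceed them. In chronic phase the effect stays at or below about 0.6 point. In blast phase the visible consequence is the median. Low severity: a descriptive secondary endpoint, a clear direction of bias and a cheap correction.

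**What to change.** In section 9.7.3, or in the statistical analysis plan under it:

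- Keep bosutinib initiation as time zero for OS, but let each patient enter the risk set on the inclusion date.
- Report, by phase, how many patients started before inclusion and the distribution of the gap.
- Repeat OS, PFS and treatment duration in patients who started at the inclusion visit. These have no gap and need no adjustment.
- Do not apply delayed entry to PFS or treatment duration in a way that drops patients whose progression or discontinuation came before inclusion, since that would hide early failures. State the rule for these patients and report their number.
- Show the Kaplan-Meier estimate without delayed entry beside the delayed-entry one.

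**Cost.** Analysis wording and a few extra outputs. The initiation date is already recorded at the inclusion visit, so no new data or visits are needed. The drawback is a smaller early risk set. In a very small blast-phase group one early death among one or two patients at risk can make the delayed-entry curve unstable, which is why both estimates should be shown.
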